5.3 Supportive Management

5.3.1 Neutropenia with or without Fever

Monitor complete blood counts throughout the treatment period. Consider supportive measures including antimicrobials for prophylaxis, in the setting of prolonged myelosuppression, and/or at the first signs of infection and use of growth factors (e.g., G-CSF). Myeloid growth factors may be used in the setting of neutropenia with or without fever as clinically indicated. Refer to Section 5.2 for guidelines on dose modifications.

5.3.2 APR-246

This section outlines the requirements for proceeding with treatment with APR-246, and the protocol rules for APR-246 dose modification due to management of QTc prolongation, CNS related AEs, nausea and vomiting, and infections.

5.3.2.1 APR-246 Dose Modification in the Setting of Moderate Renal Impairment

APR-246 is partially eliminated via the kidney and moderate renal impairment, defined by a creatinine CL or estimated glomerular filtration rate value of >30 to <60 mL/min, can lead to increases in plasma levels of approximately 30%. Therefore, for patients with moderate renal impairment, the dose of APR-246 should be reduced by 33% from the current dose (Table 7).

Table 7. APR-246 Dose Modification in the Setting of Moderate Renal Impairment

APR-246 Dose	33% Reduced Dose	Reduced Loading Dose (45mins)	Reduced Maintenance Dose (5h 15mins)
1.5 g	1.0 g	0.33 g	0.67 g
3.0 g	2.0 g	0.66 g	1.33 g
4.0 g	2.7 g	0.9 g	1.8 g

Monitoring renal function by assessment of serum creatinine prior to infusion of APR-246 is recommended in all patients.

5.3.2.2 Bone Marrow Suppression Management Guidelines

Complete blood counts should be monitored throughout the course of treatment with APR-246. Supportive measures such as antimicrobials administered for prophylaxis or in the setting of

prolonged myelosuppression, and/or at the first signs of infection are recommended to reduce the risk of a serious or severe infection that may lead to a fatal outcome in the setting of neutropenia with or without fever. Antimicrobial prophylaxis should be implemented, including appropriate prophylaxis for bacterial, viral, fungal or other types of infections or infestations (Table 8). Treatment should be individualized based on level of myelosuppression at the time of study enrollment and throughout the course of study treatment, with consideration for the patient's medical history, inclusive of prior infections.

The following recommendations were taken from National Comprehensive Cancer Network Guidelines for Prevention and Treatment of Cancer-Related Infections (Version 1.2021).

Table 8. Recommendations for Prevention and Treatment of Cancer-Related Infections

Organism	Recommendations
Bacterial	Consider fluoroquinolone or other suitable anti-bacterial prophylaxis during neutropenia
Fungal	Consider prophylaxis during neutropenia and for anticipated mucositis. Assess risk for Pneumocystis jirovecii pneumonia and select agent(s) as clinically indicated.
Viral	Start treatment with anti-viral medication in the setting of neutropenia and continually assess the risk for viral infection during treatment with anti-cancer therapy.

Myeloid growth factor may be used in the setting of severe or prolonged neutropenia. The use of blood products, including packed red blood cells (PRBCs) and platelet transfusions, are permitted and to be given at the discretion of the treating physician. Recommended guidelines for transfusion include a platelet threshold of $10 \times 10^9/L$ for platelet transfusion and a hemoglobin threshold of 8.0 g/dL for PRBC transfusion or as clinically indicated at the discretion of the treating physician.

5.3.2.3 Management Guidelines for QTc Prolongation

At screening, 12-lead ECGs should be collected in triplicate to confirm QTcF interval does not exceed 470 msec. The mean QT interval must be calculated from three ECG readings using Fridericia's correction ($QTcF = QT/RR^{0.33}$).

During APR-246 monotherapy lead-in period, and first cycle of combination therapy (venetoclax ramp-up), ECG should be collected in triplicate within 30 minutes prior to the infusion of APR-246 and within ± 30 min of end of the 6-hour infusion on all days APR-246 is administered (Days 1 and 2 of the APR-246 monotherapy lead-in, and Day 1, 8, 15 of Cycle 1). QTcF must be calculated from a mean of all three ECG readings.

On Day 2 of the APR-246 monotherapy lead-in period, ECG will be obtained prior to PO administration of APR-246, and then 6 hours after APR-246 administration.

If a pre-dose ECG shows $QTcF \geq 470$ msec, the QTc reading should be confirmed by manual assessment using Fridericia's correction ($QTcF = QT/RR^{0.33}$), unless due to BBB and/or pacemaker. Serum concentrations of electrolytes should be monitored and corrected, if necessary. Additionally, concomitant medication should be reviewed and adjusted, if necessary. ECG may be repeated at any time, including the same day. APR-246 may only be administered when QTcF has returned to <470 msec, unless due to BBB and/or pacemaker. If APR-246 is given on the same day, procedures

outlined in the Schedule of Study Evaluations must be followed. If APR-246 cannot be administered on the same day, that dose must be omitted from the cycle.

If there is a significant change in QTcF, defined as either: a) increase >60 msec from baseline (or pre-dose), or b) increase to an absolute value ≥ 501 msec, i.e., consistent with NCI-CTCAE grade 3 QTc prolongation, QTc prolongation must be confirmed by a manual assessment of the ECG, and using Fridericia's correction ($QTcF = QT/RR^{0.33}$). If confirmed, APR-246 should be interrupted until a cause (electrolyte disorders or an effect of a concomitant medication) has been identified and addressed, and QTcF has returned to <470 msec, or baseline in patients with BBB and/or pacemaker. If all other causes for clinically significant QT interval prolongation are excluded, APR-246 may be permanently discontinued. Please consult with study Medical Monitor for discussion when clinically significant QT interval prolongation is identified in a patient receiving APR-246.

During subsequent cycles, ECG should be collected in triplicate prior to infusion of APR-246 and at end of infusion (EOI) on Day 1 of each cycle. QTcF must be calculated from the mean of all three ECG readings to confirm it does not exceed 469 msec for the cycle to be initiated. If post-dose ECG shows a significant change in QTcF, defined as either: a) increase >60 msec from baseline (or pre-dose), or b) increase to an absolute value ≥ 501 msec, i.e., consistent with NCI-CTCAE grade 3 QTc prolongation, QTc prolongation must be confirmed by a manual assessment of the ECG, and using Fridericia's correction ($QTcF = QT/RR^{0.33}$). If confirmed, the therapy should be interrupted until a cause (electrolyte disorders or an effect of a concomitant medication) has been identified and addressed, and QTcF has returned to <470 msec, unless due to BBB and/or pacemaker. If all other causes for clinically significant QT interval prolongation are excluded, APR-246 may be permanently discontinued. Please consult with study Medical Monitor for discussion when clinically significant QT interval prolongation is identified in a patient receiving APR-246. If QTcF is unchanged or there is no significant change, additional ECG is not required during that cycle.

Table 9. Management Guidelines for QTc Prolongation

ECG	QTcF <450 msec	QTcF = 450-469 msec	QTcF = 470-500 msec	QTcF ≥501 or absolute increase >60 msec
Pre-dose^a	No action required. APR-246 may be administered.	APR-246 may be administered, and additional triplicate ECG should be collected at the EOI (6 hours after start of infusion, ±30 min)	QTc reading should be confirmed by manual assessment, unless due to BBB and/or pacemaker. Review serum concentrations of electrolytes and concomitant medications and adjust if necessary. ECG may be repeated at any time, including the same day. APR-246 may be administered when QTcF has returned to <470 msec, unless due to BBB and/or pacemaker. If APR-246 cannot be administered on the same day, that dose should be omitted from the cycle.	
Post-dose	No action required			If QT prolongation confirmed by manual assessment, APR-246 should be interrupted until a cause has been identified and addressed, and QTcF has returned to <470 msec or baseline value for patient with BBB or pacemaker. If all other causes for clinically significant QT interval prolongation are excluded, APR-246 may be permanently discontinued. Please consult study Medical Monitor to discuss patient's condition.

^a During APR-246 monotherapy lead-in, ECG should be collected in triplicate within 30 minutes prior to the infusion of APR-246 and within ±30 min of end of the 6-hour infusion (EOI) of APR-246 on Days 1 – 2. QTcF must be calculated from a mean of all three ECG readings.

If a patient starts treatment with a medication associated with QT interval prolongation, such as triazole antifungals, fluoroquinolones, and anti-emetics, while receiving study treatment, an additional pre- and post-dose (within 30 minutes prior to the infusion of APR-246 and within ±30 min of 6 hours after start of infusion) ECG should be performed on the next APR-246 treatment day.

5.3.2.4 Management Guidelines for APR-246 Dose Modifications and Criteria for Treatment Interruption and Re-Initiation with Treatment-Related Adverse Events

Table 10. Recommendations for APR-246 Dose Modifications and Criteria for Treatment Interruption and Re-Initiation with Treatment-Related Adverse Events

Renal Toxicities

Parameter	Worst toxicity ¹	Dose Modifications for APR-246
Serum Creatinine	Grade 1 (<1.5 × baseline)	Maintain dose level
	Grade 2 (>1.5-3.0 × baseline)	Omit dose until resolved to grade ≤1, then: If first occurrence, then maintain dose level If second or more consecutive occurrence, then ↓ 1 dose level
	Grade 3 (>3.0-6.0 × baseline)	Omit dose until resolved to grade ≤1, then: ↓ 1 dose level If not resolved or resolved in >7 days, evaluate if other contributing factors are present. If none, or after consideration of best interest of the patient, discontinue patient from APR-246. If other factors present, consider continuing after ↓ 1 dose level
	Grade 4 (>6.0 × baseline)	Permanently discontinue patient from APR-246

¹ Common Terminology Criteria for Adverse Events (CTCAE) version 5.

Hepatic Toxicities ¹

Parameter	Worst toxicity ²	Dose Modifications for APR-246
Bilirubin ³	Grade 1 (>ULN-1.5×ULN)	Maintain dose level with LFTs ⁴ monitored as per protocol
	Grade 2 (>1.5-3.0×ULN) with ALT or AST ≤3.0×ULN	Omit dose until resolved to grade ≤1, then: If resolved in ≤7 days, if first occurrence, then maintain dose level If second or more consecutive occurrence or if resolved in >7 days, then ↓ 1 dose level
	Grade 3 (>3.0-10.0×ULN) with ALT or AST ≤3.0×ULN	Omit dose until resolved to grade ≤1, then: If resolved in ≤7 days, ↓ 1 dose level. If no subsequent event, consider re-escalation to original dose level. Omit dose until resolved to grade ≤1, then: ↓ 1 dose level. If second or more consecutive occurrence or if not resolved or resolved in >7 days, evaluate if other contributing factors are present. If none, or after consideration of best interest of the patient, discontinue patient from APR-246. If other factors present, consider continuing after ↓ 1 dose level.
	Grade 4 (>10.0×ULN)	Permanently discontinue patient from APR-246

Parameter	Worst toxicity ²	Dose Modifications for APR-246
AST or ALT	Grade 1 (>ULN-3.0×ULN if baseline was normal; 1.5-3.0 × baseline if baseline was abnormal)	Maintain dose level with LFTs ⁴ monitored per protocol
	Grade 2 (>3.0-5.0×ULN if baseline was normal; >3.0-5.0 × baseline if baseline was abnormal) in the absence of total bilirubin elevation to > 2.0×ULN	Omit dose until resolved to grade ≤1, then If resolved in ≤7 days, if first consecutive occurrence, then maintain dose level If second or more consecutive occurrence or if resolved in >7 days, then ↓ 1 dose level
	Grade 3 (>5.0-20.0×ULN if baseline was normal; >5.0-20.0 × baseline if baseline was abnormal) in the absence of total bilirubin elevation to >2.0×ULN	Omit dose until resolved to grade ≤1, then If resolved in ≤7 days, if first consecutive occurrence, then maintain dose level. If second or more consecutive occurrence or if not resolved or resolved in >7 days, evaluate if other contributing factors are present. If none, or after consideration of best interest of the patient, discontinue patient from APR-246. If other factors present, consider continuing after ↓ 1 dose level
	Grade 4 (>20.0×ULN if baseline was normal; >20.0 × baseline if baseline was abnormal)	Permanently discontinue patient from APR-246

¹ Please note that the Investigator is responsible for determining whether a patient meets potential Hy's Law (PHL) criteria at any point during the study. Hy's law identifies patients at risk for severe drug-induced liver injury and is defined as AST or ALT ≥3× ULN together with Total Bilirubin Level ≥2×ULN, where no other reason, other than the suspected drug, can be found to explain the combination of increases, e.g., elevated ALP indicating cholestasis, viral hepatitis, or another drug.

² Common Terminology Criteria for Adverse Events (CTCAE) version 5.

³ For patients with Gilbert's syndrome, these dose modifications apply to changes in direct bilirubin only.

⁴ LFTs include albumin, ALT, AST, total bilirubin (fractionated if total bilirubin >2.0×ULN), alkaline phosphatase.

Other Non-Hematological Toxicities

Toxicity	Worst toxicity ¹	Dose Modifications for APR-246
Infusion-Related Reaction	Grade 1	Maintain dose level.
	Grade 2	Maintain dose level; Symptomatic management (e.g., antihistamines, corticosteroids, narcotics, IV fluids)
	Grade 3	If resolved (to grade ≤1) in <4 hours with treatment interruption and medical therapy (e.g., antihistamines, corticosteroids, narcotics, IV fluids), continue same dose level and rate. If not resolved in < 4 hours despite treatment interruption and maximal medical therapy, stop infusion and ↓ 1 dose level for subsequent dose
	Grade 4	Permanently discontinue patient from APR-246.
	Grade 1	Maintain dose level. Monitor subject and provide supportive care measures as clinically indicated.
Nausea, Vomiting, and/or Diarrhea	Grade 2	Interrupt APR-246 dosing and monitor subject; treat promptly. Resume at current dose level if toxicity resolves to grade ≤1 or baseline, with or without use of supportive care measures, within 72 hours of onset. If toxicity does not resolve to grade ≤1 within 72 hours despite maximal medical intervention(s), then reduce APR-246 by 1 dose level once the

Toxicity	Worst toxicity ¹	Dose Modifications for APR-246
		toxicity resolves to grade ≤ 1 or baseline. If unable to reduce APR-246 dose, discuss with study Medical Monitor before resuming or discontinuing treatment. For subsequent doses of APR-246, pre-medication with prophylactic supportive therapy should be given if clinically indicated.
	Grade 3	
1st occurrence: Interrupt APR-246 dosing and monitor subject; treat promptly.
 
Resume at current dose level if toxicity resolves to grade ≤ 1 or baseline, with supportive care measures, within 72 hours of onset.
 
If toxicity does not resolve to grade ≤ 1 within 72 hours despite maximal medical intervention(s), then reduce APR-246 by 1 dose level once the toxicity resolves to grade ≤ 1 or baseline.
 
If unable to reduce APR-246 dose, discuss with study Medical Monitor before resuming or discontinuing APR-246.
 
For subsequent doses of APR-246, pre-medication with prophylactic supportive therapy should be given.
 
2nd occurrence: Interrupt APR-246 dosing and monitor subject; treat promptly.
 
Reduce APR-246 by 1 dose level if the toxicity resolves to grade ≤ 1 or baseline within 72 hours of onset.
 
If toxicity does not resolve to grade ≤ 1 despite maximal medical intervention(s) within 72 hours of onset, then consult with study Medical Monitor before resuming or discontinuing APR-246.
 
If unable to reduce APR-246 dose, discuss with study Medical Monitor before resuming or discontinuing treatment.
 
Prior to subsequent doses of APR-246, reassess prophylactic supportive therapy regimen and adjust as clinically indicated.
 
3rd occurrence: Interrupt APR-246 dosing and monitor subject; treat promptly. Consult with study Medical Monitor before resuming or discontinuing APR-246.

	Grade 4	Interrupt APR-246 dosing and monitor subject; treat promptly. Consult with study Medical Monitor to discuss dose modification or permanent discontinuation of APR-246.
Any Other Toxicity	Grade 3 or 4	
Delay dose until resolution to grade ≤ 1 or baseline, then $\downarrow 1$ dose level.
 
If unable to reduce APR-246 dose, discuss with study Medical Monitor before resuming or discontinuing APR-246.

¹ Common Terminology Criteria for Adverse Events (CTCAE) version 5.

Treating physicians should use clinical judgment and may consult the Medical Monitor for additional guidance with APR-246 dose modifications.

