Occurrence	APR-246	Venetoclax	Rituximab
1 st occurrence • Hold all study treatments until toxicity returns to baseline or grade ≤1. Treat promptly.	
Consider reducing APR-246 by one dose level from current dose for all future cycles of treatment if toxicity does not resolve to grade ≤1 within 7 days from onset date despite maximal medical intervention(s).If unable to reduce APR-246 dose, discuss with study Medical Monitor before resuming or discontinuing treatment.	Refer to Section 5.3.3.1 for venetoclax dose modification guidelines.	Resume rituximab at same dose level once event resolves to baseline or grade ≤1, except in case of serious infection. For patients diagnosed with a serious grade ≥3 infection, rituximab should be permanently discontinued.
2 nd occurrence • Hold all study treatments until toxicity returns to baseline or grade ≤1	
Consider reducing APR-246 by one dose level from starting dose for all future cycles of treatment.	Refer to Section 5.3.3.1 for venetoclax dose modification guidelines.	Reduce rituximab dose from 500 mg/m ² to 375 mg/m ² . If unable to reduce rituximab, discuss with study Medical Monitor before resuming or discontinuing rituximab. For patients diagnosed with serious grade ≥3 infection, rituximab should be permanently discontinued.
3 rd occurrence • Hold all study treatments until toxicity returns to baseline or grade ≤1. Treat promptly.	
Consult with study medical monitor to determine if further dose modifications of study treatment(s) are medically necessary or if study treatment(s) should be discontinued.		

Actions noted in table above for rituximab are specific to toxicities occurring during Cycles 2 through 7. Rituximab may be reduced by one dose level, from 500 mg/m² to 375 mg/m², when clinically indicated. Please consult with study Medical Monitor to discuss dose modification(s) for rituximab.

Treatment may be discontinued if a TEAE has not improved (to an acceptable grade) or resolved after ≥ 4 weeks, at the discretion of the Investigator. Please consult study Medical Monitor if this situation occurs.

Patients experiencing 3 occurrences of the same toxicity should be discussed with the study Medical Monitor before study treatments are resumed.

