7.5 Electrocardiographic Assessment

[Table 19](#) describes the routine ECG requirements.

Table 19. ECG Assessment Requirements

Time Point	ECG, number	Timing
Baseline/Screening	TriPLICATE	Within 28 days of study treatment ¹
APR-246 Monotherapy Lead-In	TriPLICATE	Pre-dose; at the end of the infusion (± 30 min) ²
Cycle 1, Day 1, 8 and 15	TriPLICATE	Pre-dose; at the end of the infusion (± 30 min)
Cycles 2+, Day 1	TriPLICATE	Pre-dose; at the end of the infusion (± 30 min)
End of Treatment	TriPLICATE	Within 28 days of the last dose of APR-246

¹ Baseline/Screening registration is for eligibility purpose and should be performed before the patient is approved and registered in IWRS to start any treatment on study, i.e., 28 days prior to the first dose of venetoclax in ramp-up.

² On Day 2 of the APR-246 monotherapy lead-in period, ECG is obtained prior to PO administration of APR-246, and then 6 hours after APR-246 administration.

If repeated QTcF measurements show a stable QTcF < 470 msec, unless due to BBB and/or pacemaker, with no significant change at the EOI during several cycles of treatment, reducing the number of ECGs performed in the study may be discussed with the Medical Monitor.

If a patient starts treatment with another medication known to prolong QT interval at any time during the study therapy, an additional pre- and post-dose (6 hours after start of infusion, ± 30 min) ECG should be performed on the next treatment day.

Please consult Section [5.3.1](#) for additional requirements for proceeding with treatment with APR-246.

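### After a QTcF rise of more than 60 msec, Section 5.3.2.3 lets APR-246 restart at QTcF below 470 msec with the rise still present, which is looser than Tables 6 and 10

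*Combined protocol and SAP*

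**What the plan says.** Section 5.3.2.3 has two paragraphs on post-dose QTcF, one for the lead-in and Cycle 1 and one for later cycles. Table 9 summarises them. Both paragraphs define a significant change in two alternative ways: an "increase >60 msec from baseline (or pre-dose"), or a value of 501 msec or more. Both then describe the change as consistent with CTCAE grade 3 and require manual confirmation.

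The release is the same for either trigger. In Table 9, "APR-246 should be interrupted until a cause has been identified and addressed, and QTcF has returned to <470 msec". The lead-in and Cycle 1 paragraph makes one exception: "QTcF has returned to <470 msec, or baseline in patients with BBB and/or pacemaker". If all other causes are excluded, APR-246 may be stopped permanently. The Medical Monitor is to be consulted.

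Two general rules also cover severe non-hematologic toxicity. Table 6, which Section 5.2 says should be followed, states for grade 3 or 4 events: "Hold all study treatments until toxicity returns to baseline or grade" 1 or lower. Table 10 (Section 5.3.2.4), in its row for any other grade 3 or 4 toxicity, states: "Delay dose until resolution to grade" 1 or lower, or baseline, followed by a reduction of one dose level.

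**The concern.** One trigger is relative to the patient and the other is absolute, but they share one absolute release number. A return to below 470 msec is a real recovery test for someone who reached 501. It is no test for someone whose QTcF rose by more than 60 msec without reaching 470. For that patient the numeric condition is already met, and nothing in Section 5.3.2.3 asks whether the rise has gone.

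What is at stake is a cardiac safety hold. A site that follows the QTc section literally could re-dose while the change that stopped dosing is still present. A site that follows Table 6 or Table 10 for the same event could not.

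**Working it through.** The plan states no figure to reproduce. The check applies the stated thresholds in whole msec, with R as the reference QTcF.

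**Inputs**
- Relative trigger: post-dose QTcF - R > 60, so the first triggering value is R + 61 (Section 5.3.2.3, Table 9).
- Absolute trigger: post-dose QTcF of 501 or more (same places).
- Numeric release, no bundle branch block or pacemaker: QTcF < 470, so at most 469 (same places).
- R itself is illustrative. The documents as available give no QTcF distribution.

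**Step 1: when the release number can be met as the hold starts.** This needs R + 61 ≤ 469, so R ≤ 469 - 61 = 408. At R = 409 the first triggering value is 470, and a fall is needed.

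**Step 2: rise remaining at the highest releasable value.** This is 469 - R.

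**Step 3: effect of also requiring that the rise no longer exceed 60 msec.** The re-dosing ceiling becomes min(469, R + 60).

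| R | Triggering values already below 470 | Rise left at 469 | Ceiling with the added condition | Reduction |
|---|---|---|---|---|
| 375 | 436-469 | 469 - 375 = 94 | 435 | 34 |
| 390 | 451-469 | 469 - 390 = 79 | 450 | 19 |
| 400 | 461-469 | 469 - 400 = 69 | 460 | 9 |
| 408 | 469 | 469 - 408 = 61 | 468 | 1 |
| 409 | none | 469 - 409 = 60 | 469 | 0 |

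Step 3 is the minimum repair. Return to baseline or grade 1 or lower, as in Tables 6 and 10, may be stricter. No ceiling is computed for it, because the documents give no msec limit for grade 1.

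**Step 4: do the other conditions in Section 5.3.2.3 test the rise?**
- Finding and addressing a cause is a judgement about why QTcF rose. It does not say how far QTcF must fall.
- Consultation with the Medical Monitor has no stated criterion.
- The gate for starting a later cycle is also absolute: QTcF may not exceed 469 msec. A patient with R = 400 passes it at +69.
- The later-cycle paragraph says: "If QTcF is unchanged or there is no significant change, additional ECG is not required during that cycle". This implies a further ECG after a significant change, but gives neither its timing nor a pass mark for the rise.

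**Step 5: comparison with the general rules.** Section 5.3.2.3 requires below 470 msec plus an addressed cause. Tables 6 and 10 require baseline or grade 1 or lower. If a rise of more than 60 msec is a grade 3 event, as the section's own description suggests, the two sets of rules give different conditions for restarting after the same event.

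**The case against.** The strongest reply is that the general rules already close the gap. The trigger sentence ends by calling the change consistent with grade 3, and Table 9 puts both triggers in one column. Section 5.2 says that Table 6 should be followed. Table 10 lies inside Section 5.3.2, whose introduction says that it contains "the protocol rules for APR-246 dose modification due to management of QTc prolongation". On this reading nothing is missing except a cross-reference. Much of this stands: a reader might infer that the protocol has no adequate release rule, and the documents do not support that. What remains is a conflict. The QTc-specific text and table are what a site would open for a QTc event, and they give the looser condition without pointing to the stricter one. The grade 3 phrase could also be read as attaching only to the 501 msec limb.

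Four other strong readings are tempting and not supported.
- **That the hold lapses at once.** It does not. A cause must be addressed, and if all others are excluded APR-246 may be stopped. For references of 409 or more, and for the 501 msec trigger, the 470 limit does real work.
- **That a held patient would be re-dosed without an ECG.** Routine ECGs in Cycles 2 and beyond are on Day 1 only (Table 19), but a return to below 470 is naturally read as needing a new measurement, and the later-cycle paragraph implies one.
- **That naming both baseline and pre-dose is a separate error.** Table 19 labels the screening ECG as baseline and says of it: "Baseline/Screening registration is for eligibility purpose and should be performed before the patient is approved". The two references can therefore differ. The wording nevertheless reads naturally as either one, and Section 5.3.2.3 adds pre- and post-dose ECGs on the next APR-246 day when a QT-prolonging drug is started.
- **That dose-limiting toxicity counts or cohort decisions are affected.** Nothing here shows that.

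**Conclusion.** The point holds as a conflict between a specific rule and the protocol's own general rule. It applies to patients without bundle branch block or a pacemaker, after the >60 msec trigger, at a reference of 408 msec or less. There, Section 5.3.2.3 and Table 9 numerically permit re-dosing up to 469 msec with the rise still above 60: 94 msec at reference 375, 69 at 400 and 61 at 408. At 409 and above the problem disappears.

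The arithmetic is exact and assumes only whole-msec readings. How often such cases would arise cannot be estimated, because the cardiac safety section is redacted. The conflict with Tables 6 and 10 assumes that the event is graded 3, which the section's wording supports but does not settle for the relative limb. The text should be corrected. The cause requirement and the Medical Monitor's involvement make the defect limited, not critical.

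**What to change.** In both post-dose paragraphs of Section 5.3.2.3 and in the Table 9 post-dose cell, state that after a >60 msec trigger APR-246 may resume only when all of these are met:
- the cause requirement, unchanged;
- QTcF below 470 msec;
- the rise has resolved to baseline or grade 1 or lower, and at minimum is no longer more than 60 msec above the reference that triggered the hold.

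The QTcF conditions should be shown on a repeat ECG before the next APR-246 dose. Add a cross-reference to Tables 6 and 10. Because Table 10 also reduces the dose by one level, say whether that reduction applies. The existing baseline exception for bundle branch block or pacemaker can stay. Writing that either baseline or pre-dose may trigger the hold is an optional clarification.

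The cost is the wording of one section and one table cell, with no added patients or visits. Some holds will last longer. Cycle 1 infusions already have a pre-dose ECG. In later cycles a held patient may need a repeat ECG at an existing Day 8 or Day 15 visit. The threshold values remain the sponsor's choice.
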